PROJECT DESCRIPTION

Title: Attenuation of Stress Response Using Progesterone in Individuals with Alcohol Dependence and Post-Traumatic Stress Disorder NCT02187224

1. Principal Investigator:

[name]

Authorized Prescribers: [name] MD, [name] MD, [name] MD, [name] MD

2. Purpose:

Primary Aims:

1. To test if progesterone (PROG) is more effective than placebo in reducing craving after exposure to trauma or stress cues in a laboratory paradigm among men and women with a) comorbid AUD and PTSD and b) AUD only.

We hypothesize that progesterone in comparison to placebo will significantly reduce craving for alcohol in response to trauma cues in individuals with a) comorbid AUD and PTSD and b) AUD only. Craving for alcohol will be measured using a self-report Visual Analog Scale - Craving (VASC) and the Alcohol Urge Questionnaire (AUQ).

Secondary Aims:

1. To test if progesterone attenuates stress-induced anxiety, measured by the State Trait Anxiety Inventory (STAI-6).

2: To describe PROG's subjective mood effects, we will use the Differential Emotion Scale (DES-R)

3: To describe PROG's effects on cognitive performance, we will assess the ability to inhibit incongruent competing conflicts using the Stroop Color/Word test (Stroop).

Exploratory Aims:

1. To test if progesterone is more effective than placebo in reducing drinking and relapse during one month following exposure to trauma cues *using the Timeline Follow Back Method (TLFB)*.

2. To examine if there are gender differences in progesterone effects on stress and alcohol cue-induced craving.

We hypothesize that the effects of progesterone on stress and craving will be stronger in women than in men.

3. Background:

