Results: Dually diagnosed veterans reported significantly more craving for alcohol when exposed to trauma imagery than when exposed to stressful or neutral imagery ($p<0.001$) (Figure 1). The stress response decreased with treatment, and those with high stress response on prazosin reported greater, but not statistically significant, change in their drinking at the end of treatment (Figure 2). Also, there was a significant relationship ($r=0.603$) (Figure 3) between craving and the number of drinking days at follow up.

Conclusions: The preliminary findings show that veterans with dual diagnosis report strong craving after exposure to trauma

related imagery. **Based on this result we eliminated the stress condition for the present study.** The trauma-induced response predicted drinking at the end of treatment and at follow up.

- *These finding support the notion that reactivity to stress may increase the susceptibility for relapse.*
- *This study demonstrates that we have experience with this paradigm.*
- *It validates the ability of our research team to recruit individuals with AUD and PTSD.*

4. Significance:

To our knowledge, this study is the first to examine the ability of progesterone to reduce trauma or stress-induced craving in individuals diagnosed with a) comorbid AUD and PTSD and b) AUD only. Positive findings from this study will: 1) provide evidence that progesterone is important in mediating stress and alcohol craving, 2) provide insight into the underlying mechanisms of stress and alcohol craving, 3) help identify a potential marker that will distinguish who may be at

higher risk for alcohol relapse, and 4) provide a platform for other exploratory studies that can include the use of progesterone as treatment options for AUD and PTSD.

5. Research Plan:

Participants: Participants (N=72 completers) will be eligible for the study if they fullfill the following criteria:

Inclusion criteria:

- a) men (n=36) and women (n=36) age 21 to 60;
- b) have current diagnosis of *either*:
 - 1. AUD and comorbid PTSD
 - OR
 - 2. AUD

AUD will be determined by Structured Clinical Interview for DSM-5 (SCID-5) (First, Spitzer, Gibbon, & Williams, 2015). PTSD will be determined by Clinician Administered PTSD scale (CAPS-5)(Weathers et al., 2013) and by SCID-5);

- c) drink regularly (determined by TLFB and recorded 90 days prior to the interview);
- d) are not in an active phase of alcohol withdrawal;

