Initial Assessments: Participants will be interviewed with the SCID and CAPS for diagnostic evaluation. The TLFB(Sobell & Sobell, 1992) will be used to document the degree of daily alcohol consumption in the three months prior to study entry. Participants will have a psychiatric and medical examination by one of the investigators. Study data will be collected and managed using REDCap electronic data capture tools hosted at VA CT Healthcare System. REDCap

(Research Electronic Data Capture) is a secure, web-based application designed to support data capture for research studies, providing 1) an intuitive interface for validated data entry; 2) audit trails for tracking data manipulation and export procedures; 3) automated export procedures for seamless data downloads to common statistical packages; and 4) procedures for importing data from external sources (Harris et al 2009).

Screening and Baseline: Each participant will sign an informed consent. The study will be conducted with the approval of the VA Connecticut Human Subject Subcommittee. As part of the screening procedure detailed clinical assessment (to determine diagnosis), and medical assessments (physical exam, medical history, blood work and electrocardiogram) will be conducted. Those participants who fulfill all the inclusion and exclusion criteria will be enrolled in the study. On the first visit participants will be asked to come for a script development session. Also, women will be instructed to call the clinic when their menses starts and begin taking the study medication within the first 4 days of their menstrual cycle. The procedure is implemented in order to give some flexibility to female subjects and to ensure that they can finish the study during the early follicular phase (within the first seven days of the menstrual cycle).

Script Development Session: Scripts will be developed during a visit prior to the first laboratory session. Two scripts will be developed for each participant based on a procedure developed by our group. Participants with AUD and comorbid PTSD will develop one trauma related script and one neutral script. Participants with AUD only will develop one stress related script (since they have not experienced trauma) and one neutral script.

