Laboratory sessions: Laboratory sessions will be conducted on the Biological Studies Unit at the West Haven VA with trained personnel, and a psychologist or MD will be on call during the laboratory session. Additionally, all participants will be cleared by a study doctor prior to leaving the lab at the end of the imagery session (see Table 1 for details). Participants will be asked to arrive around 10:00 am. On arrival there will be a urine and breath alcohol concentration (BrAC) check. If clear to start an IV line will be placed. Those who test positive for any substance (other than marijuana) will be discharged. Blood pressure and pulse will be monitored continuously. Subjective measures of craving for alcohol, anxiety, affect, and cognitive functioning will be administered shortly after the set up. Prior to the presentation of the 1st and 2nd tapes, the relaxation technique will be used. Two conditions will be administered in a counterbalanced order: Trauma/Stress script and Neutral script. Subjective measures of craving, anxiety, affect, and cognitive functioning will be presented:1) prior to presentation of the scripts, b) immediately after presentation of each script, and c) following a 5 minute recovery period. After the last recovery period and assessments subjects will be encouraged to use the relaxation techniques. Craving and emotional distress will be evaluated throughout the session and subjects must return to baseline levels prior to being discharged from the unit. Subjects will wear an ambulatory physiological monitor (APM) (Eqvital EQ02, Vivonoetics, San Diego, CA) that collects continuous ECG, respiration, and activity for 20 minutes while at quiet rest at baseline, and throughout the stress challenge procedure. After completion of the scheduled portion of a session, any subject that reports residual craving or distress will participate in guided relaxation procedures with a clinically-trained psychologist for up to one additional hour. Relaxation has also been shown to reduce PTSD symptoms(Hamid & Neissi, 2009). If craving or emotional distress persists after an hour of relaxation training, the subject will receive an individual counseling session with a psychologist who is experienced in psychotherapy for PTSD. If craving or emotional distress persists after the psychotherapy session, the subject will be escorted to the Emergency Department and treated by the on-call psychiatrist.

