Method for data collection and analyses: Prior to performing statistical analyses, we will calculate descriptive statistics and will assess whether the distributions of all measures conform to normality. We will apply transformation or use nonparametric methods as necessary. We will estimate effect sizes in order to inform the design of potential future definitive studies. For the primary hypotheses we will use mixed effects models to assess change in stress reactivity after administration of progesterone vs. placebo. Study medication (progesterone and placebo), and gender will be a between subject factors, condition (trauma vs neutral) and time (pre, post and recovery following script presentation) will be used as within-subject factors. The primary stress reactivity variables will be craving. We will first compute descriptive statistics for each variable and will assess data distributions. All tests will be two-sided at 0.05 level of significance. We will use the Schwartz-Bayesian criterion (BIC) to select the best-fitting correlation structure within subject.

Study Duration: Two years.

6. References:

Allen, M. T., Boquet, A. J., Jr., & Shelley, K. S. (1991). Cluster analyses of cardiovascular responsivity to three laboratory stressors. *Psychosomatic Medicine*, 53(3), 272-288.

Blake, D. D., Weathers, F. W., Nagy, L. M., Kaloupek, D. G., Klauminzer, G., Charney, D. S., & Keane, T. M. (1990). A clinician rating scale for assessing current and lifetime PTSD: The CAPS-1. *Behavior Therapy*, 13, 187-188.

Bohn, M. J., Krahn, D. D., & Staehler, B. A. (1995). Development and initial validation of a measure of drinking urges in abstinent alcoholics. *Alcoholism, Clinical and Experimental Research*, 19(3), 600-606.

Brady, K. T., Killeen, T., Saladin, M. E., Dansky, B., & Becker, S. (1994). Comorbid Substance-Abuse and Posttraumatic-Stress-Disorder - Characteristics of Women in Treatment. *American Journal on Addictions*, 3(2), 160-164.

Breese, G. R., Chu, K., Dayas, C. V., Funk, D., Knapp, D. J., Koob, G. F., . . . Weiss, F. (2005). Stress enhancement of craving during sobriety: a risk for relapse. *Alcoholism, Clinical and Experimental Research*, 29(2), 185-195.

Bremner, J. D., Krystal, J. H., Southwick, S. M., & Charney, D. S. (1996). Noradrenergic mechanisms in stress and anxiety: II. Clinical studies. *Synapse*, 23(1), 39-51. doi: 10.1002/(SICI)1098-2396(199605)23:1<39::AID-SYN5>3.0.CO;2-1

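### The primary hypothesis and the model's condition factor name trauma cues for everyone, but AUD-only participants hear a stress script, and no result is specified for each diagnosis

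*Combined protocol and SAP*

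**What the plan says.** Primary Aim 1 (Purpose) asks whether progesterone beats placebo "in reducing craving after exposure to trauma or stress cues in a laboratory paradigm", in (a) AUD with PTSD and (b) AUD only. The hypothesis that follows narrows the cue: progesterone is expected to "reduce craving for alcohol in response to trauma cues in individuals with a) comorbid AUD and PTSD and b) AUD only".

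The Script Development Session section assigns scripts by diagnosis. For the comorbid group: "Participants with AUD and comorbid PTSD will develop one trauma related script and one neutral script". For the other: "Participants with AUD only will develop one stress related script (since they have not experienced trauma) and one neutral script". The Laboratory sessions section keeps both cue types in view: "Two conditions will be administered in a counterbalanced order: Trauma/Stress script and Neutral script".

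Method for data collection and analyses specifies mixed effects models with medication and gender between subjects, and "condition (trauma vs neutral) and time (pre, post and recovery following script presentation) will be used as within-subject factors". Neither the stress script nor diagnosis appears in that model.

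**The concern.** The hypothesis and the model are what will be tested and reported, and both carry a cue label that is wrong for one of the two primary populations. An analyst following the model text either files stress-script responses under trauma or has nowhere to put them. With no diagnosis factor, the output is one medication effect over both populations, although the primary aim names (a) and (b) separately.

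At stake is what the trial can claim. A report could state an effect on trauma-cue craving for people who never heard a trauma cue. A pooled null could not be traced to one cue or the other. If the label and the per-diagnosis estimates are settled only after the data are seen, the choice is open to the results.

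**Working it through.** **1. Cue named in each place.**

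| Section | AUD with PTSD | AUD only |
|---|---|---|
| Purpose, Primary Aim 1 | trauma or stress | trauma or stress |
| Purpose, hypothesis | trauma | trauma |
| Significance | trauma or stress | trauma or stress |
| Script Development Session | trauma, neutral | stress, neutral |
| Laboratory sessions | trauma/stress, neutral | trauma/stress, neutral |
| Analysis methods, condition factor | trauma, neutral | trauma, neutral |

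Two rows do not fit the script assignment for AUD only: the hypothesis and the condition factor. No section gives an AUD-only participant a trauma script or a comorbid participant a stress script.

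**2. What the model estimates as written.** Let w be the share of participants with PTSD, T the drug effect on trauma-minus-neutral craving in that group, and S the drug effect on stress-minus-neutral craving in AUD only. Without a diagnosis factor, the medication-by-condition term estimates roughly w·T + (1 − w)·S. It is neither T, the answer for (a), nor S, the answer for (b). The plan fixes neither w nor the ratio of S to T.

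**3. Whether adding diagnosis separates PTSD from script type.** Take the 2 × 2 × 2 = 8 cells of diagnosis, drug, and active versus neutral script. The full factorial design matrix has rank 8. Adding columns for script type and drug-by-script-type leaves the rank at 8. The diagnosis-by-active-script column is identical to the trauma-script column, and diagnosis-by-drug-by-active-script is identical to drug-by-trauma-script. T and S can each be estimated, but the difference T − S cannot be split into a PTSD part and a stimulus part. Baseline and neutral-script differences are not affected, since both groups hear a neutral script.

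**4. Precision cost of reporting by diagnosis.** The Power Analysis gives n = 30 for 80% power at d' = 0.50, two-sided alpha 0.05, as a within-subject comparison. A paired normal approximation gives n = ((1.960 + 0.842)/0.50)² = 31.4, so 32, and power at n = 30 of Φ(0.50·√30 − 1.960) = Φ(0.779) = 78%. The stated figure is thus roughly reproduced in its own terms. The drug comparison here is between subjects, so the figures below use a two-sample t test on a difference score.

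Assume equal arms and equal diagnosis groups (the plan states no split). The 72 completers under Participants give 72/4 = 18 per arm per diagnosis, and 36 per arm pooled. If instead 30 of each 36 complete, as in the Power Analysis, 60/4 = 15 and 30.

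| Comparison | n per arm | Power at d = 0.50 | d detectable with 80% power |
|---|---|---|---|
| Pooled | 36 (30) | 55% (48%) | 0.67 (0.74) |
| One diagnosis | 18 (15) | 31% (26%) | 0.96 (1.06) |

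The standard error is proportional to √(2/n), so the ratio is √(36/18) = 1.41. The mixed model may do somewhat better; these values only indicate scale.

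**The case against.** The strongest reply is that the intention is clear from the rest of the document. The aim one sentence earlier, the Significance section, the script assignment and the laboratory procedure all recognise a stress cue for AUD only, so trauma in the hypothesis and the model reads as shorthand or leftover wording. That stands, and it makes the correction easy. It does not put the right label or a diagnosis factor into the model.

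Several stronger readings are tempting and are not supported:

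- A reader might infer that aim (b) cannot be tested. It can. Within AUD only, both arms hear the same script type, so progesterone versus placebo on stress-script craving is unconfounded. Only the trauma wording of (b) has no data.
- A reader might infer that a planned comparison is confounded. No aim compares the diagnoses. The nesting restricts interpretation only.
- A reader might take "Based on this result we eliminated the stress condition for the present study" in Preliminary Data as an unresolved contradiction. The Script Development Session section limits the removal of stress imagery to participants with both AUD and PTSD.
- A reader might infer from the pilot that stress scripts are too weak for AUD only. The pilot finding was "Dually diagnosed veterans reported significantly more craving for alcohol when exposed to trauma imagery than when exposed to stressful or neutral imagery" (p<0.001). It concerns craving level in comorbid patients, not AUD only, and says nothing about whether the drug effect differs by script. The Background cites evidence that stress cues raise craving in AUD about as strongly as alcohol cues do.
- A reader might want a percentage for how far pooling dilutes the trauma-cue effect. That needs w and the ratio of S to T, which the documents do not give.

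The precision objection also stands: estimates by diagnosis will be wide.

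**Conclusion.** The mismatch is real and lies in the primary hypothesis and the primary model. It affects every AUD-only participant; how many that is, the plan does not say. As written, the analysis mislabels their active-script responses and does not deliver the (a) and (b) results that the primary aim calls for. The drug comparison within each diagnosis is sound, and matching scripts to diagnosis is a deliberate choice, so this is a fault of specification, not a failure of the design. It should be fixed before the data are analysed, but it does not invalidate the trial. The conclusion rests on the text and on the aliasing check alone; only the precision figures depend on assumed equal groups.

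**What to change.** 1. Reword the hypothesis so that it predicts lower craving to trauma cues in (a) AUD with PTSD and to personal stress cues in (b) AUD only.
2. In the analysis section, define condition as active script (trauma in AUD with PTSD, stress in AUD only) versus neutral. Add diagnosis as a between-subject factor with its interactions with medication, condition and time. For each diagnosis, report the progesterone-placebo difference in active-minus-neutral craving with its confidence interval, labelled by cue, at a time point named in advance.
3. State that a difference between the two estimates will not be attributed to PTSD, because script type is nested in diagnosis. Report active-minus-neutral craving in the placebo arm by diagnosis, as a check that each script provoked craving.

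The trauma wording in Exploratory Aim 1 and the sentence on the dropped stress condition in Preliminary Data are clerical and can be tidied at the same time.

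No new data or procedures are needed. The costs are a larger model, one descriptive table, less precise estimates than a pooled one (about 1.41 times the standard error under equal groups), and giving up a trauma-cue claim in AUD only.

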Cardiovascular and Hormone Outcome Measures: Blood pressure and pulse will be assessed using an SD-700 monitor. To assure greater accuracy for the initial time points (baseline and time 0) four measures of blood pressure and pulse will be taken, and their average will constitute the single blood pressure and pulse measure. A single reading will be used for the other time points during testing. During the laboratory sessions we will also collect blood samples to examine the levels of allopregnanolone (ALLO) - the active metabolite of progesterone – and markers of inflammation to explore the relationship between these biomarkers and behavioral effects (urges for alcohol, anxiety, mood, cognitive functioning) of progesterone and alcohol. ECG RR intervals will be edited to remove artifact and ectopy using CardioEdit software. High and low frequency HRV will be calculated using CardioBatch software (Mind/Body Institute, U Ill Chicago).

Subject Payments: Participants will be paid \$70 for screening and diagnostic evaluation, \$80 for scripting, \$25 for each medication visit (2), \$250 for the laboratory session, and \$50 for the follow up session. Therefore, participants could earn up to \$500.

Power Analysis: Sample size estimates were determined using craving from our preliminary data. Assuming a large effect size for the within-subject comparison between progesterone and placebo ($d'=0.50$)(Cohen, 1988), $\alpha=.05$ and two-sided test, we have 80% power to detect such an effect size as statistically significant with $n=30$ subjects. Assuming 20% dropout rate we need to recruit 36 subjects in order to have complete data on 30 subjects per group.

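### The 72 in the Participants section counts completers, but the Power Analysis implies 72 recruited and 60 completing, with the 20% dropout allowance applied the wrong way round

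*Combined protocol and SAP*

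**What the plan says.** Two paragraphs of section 5, Research Plan, give the sample size.

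- **Participants and inclusion criteria.** The total is a count of people who finish: "Participants (N=72 completers) will be eligible for the study". The first inclusion criterion divides it by gender: "men (n=36) and women (n=36) age 21 to 60".
- **Power Analysis.** The target is set per group and allows for loss: "Assuming 20% dropout rate we need to recruit 36 subjects in order to have complete data on 30 subjects per group". The calculation behind the 30 uses an effect size of 0.50, described as within-subject, with two-sided alpha of 0.05 and 80% power.

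The Methods paragraph describes a between-subject comparison of progesterone and placebo. The Power Analysis does not say what a group is, and neither paragraph gives a total number recruited or randomised.

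**The concern.** The figure of 36 per group, 72 over two groups, is a number completing in one paragraph and a number recruited in the other. With any dropout these describe different trials. One continues until 72 people have finished. The other stops once 72 have entered and expects fewer to finish. The person running recruitment would not know when to stop, and a reader could not tell what number the power statement should be judged against.

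The dropout allowance adds a second, smaller inconsistency. Recruiting 36 does not deliver an expected 30 completers if one in five is lost.

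**Working it through.** **Inputs from the documents.** 72 completers, 36 men and 36 women (Participants); recruit 36 to have 30 complete per group, 20% dropout, d = 0.50, two-sided alpha 0.05 (Power Analysis); two medication arms, between-subject (Methods; Method for data collection and analyses).

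**Assumptions.** Two equal groups, and 1:1 allocation for the power figures. The documents state neither.

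**1. Reproduce the plan's 36.** n x (1 + d) = 30 x 1.20 = 36. The stated figure is recovered exactly.

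**2. Check what 36 delivers.**
- Expected completers: 36 x (1 - 0.20) = 28.8 per group, which is 1.2 short of 30.
- Loss implied by going from 36 to 30: 1 - 30/36 = 16.7%, not 20%.
- Recruits needed to keep 30: n/(1 - d) = 30/0.80 = 37.5, so 38 per group.

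**3. Compare the totals.**

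| Reading | Recruited | Completing |
|---|---|---|
| Participants section as written | not stated | 72 |
| Power Analysis as written, two groups | 2 x 36 = 72 | 2 x 30 = 60 |
| 72 recruited, 20% loss | 72 | 72 x 0.80 = 57.6 |
| 60 completing, 20% loss | 60/0.80 = 75 (76 as 2 x 38) | 60 |
| 72 completing, 20% loss | 72/0.80 = 90 | 72 |

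The gap from 72 completers is 72 - 60 = 12 on the plan's own figures, and 72 - 57.6 = 14.4 at a true 20% loss.

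**4. Try other meanings of group.** Arm, gender and diagnosis each have two levels and give the same 72 recruited and 60 completing. Four diagnosis-by-arm cells give 4 x 36 = 144 recruited and 4 x 30 = 120 completing. None of these gives 72 completers.

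**5. Effect on power.** Two-sample t test, d = 0.50, two-sided alpha 0.05:

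| Completers per arm | Power |
|---|---|
| 29 | 46.5% |
| 30 | 47.8% |
| 36 | 55.3% |

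Moving from 36 to 30 per arm costs 55.3 - 47.8 = 7.5 points. Moving from 36 to 29 costs 55.3 - 46.5 = 8.8 points. The inflation slip alone (30 against 29) costs 47.8 - 46.5 = 1.3 points.

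**6. Where the rest of the shortfall comes from.** A paired t test at d = 0.50 has 75.4% power with n = 30 and 83.1% with n = 36, which is close to the stated 80%. A two-sample t test needs 64 per arm for 80%. The fall from about 80% to about 50% therefore comes from the type of comparison, not from the completer count.

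**The case against.** The best defence is that no sentence calls 72 the number recruited. That figure is 2 x 36, and group is undefined. This is correct, and the conflict should be described as implied. It does not remove the conflict, because none of the readings tried above gives 72 completers.

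A second defence is that 36 is a familiar shortcut and lies only 2 from the correct 38. That also stands. The figure does reproduce, and the formula's error is small. The conflict between 72 and 60 completers carries the point.

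A reader might infer several stronger things that the documents do not support:

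- **That this problem explains power of 46 to 55%.** It does not. Those levels come mainly from the within-subject calculation, which is a separate matter.
- **That a low chance of reaching 30 completers proves an error.** At 20% independent loss, the chance of at least 30 completers from 36 is 40% per group. From the correct 38 it is still only 66%. The plan states an expected loss, not a guarantee.
- **That analysis will be limited to completers.** The word describes a sample-size target. The analysis paragraph specifies mixed effects models and sets no such restriction.
- **That 72 is plainly the number randomised.** The Power Analysis says recruit, and the Methods place recruitment before consent, eligibility assessment and randomisation. Whether the 20% covers screening losses is not stated.

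**Conclusion.** The point holds as an inconsistency to be reconciled. The Participants section gives 72 completers. The Power Analysis implies 72 recruited and 60 completing if there are two equal groups, or about 58 completing at a true 20% loss. The analysable sample is therefore uncertain by 12 to 14 people. The dropout formula is a minor error of 1.2 completers per group.

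The effect on power is modest, about 7 to 9 points at d = 0.50, assuming 1:1 allocation and a simple two-sample comparison. It does not invalidate the trial. The documents do not show which total was intended, so this review cannot say which paragraph is wrong.

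**What to change.** Define group in the Power Analysis. State once whether 72 is the number randomised or the number completing, and say whether the 20% is loss after randomisation. Use the same figures in both paragraphs, with dropout applied as n/(1 - d). The consistent options are:

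- **72 randomised.** About 58 are expected to complete, about 29 per arm under 1:1 allocation. The Participants section would no longer call the 72 completers. This needs no extra enrolment.
- **60 completing.** Plan for 75 randomised, or 76 as 38 per group.
- **72 completing.** The Power Analysis changes instead, to about 90 randomised (45 per group).

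Then restate power for the chosen number using a between-subject calculation.

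The first option costs only wording in two paragraphs, but the stated completer number and power become less favourable. The second costs 3 to 4 more participants than 72, and the third costs 18 more.
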